7.2.2 Secondary outcomes

- 1) The demographic characteristics of the latest visit for all patients, as well as the trends for inpatients over time (2015, 2017, and 2019 respectively). Clinical characteristics of outpatients and hospitalized patients will be described respectively.

Table 2. The demographic and clinical characteristics of the latest visit

| Outpatients | | | | Inpatients | | | | Total patients |
|--|----------------|----------------|----------------|-------------------|----------------|----------------|----------------|-----------------------|
| Group A | Group B | Group C | Group D | Group A | Group B | Group C | Group D | |
| Demographic characteristics in 2015 | | | | | | | | |
| Age (mean, sd) | | | | | | | | |
| Gender (n, %) | | | | | | | | |
| Insurance payment (n, %) | | | | | | | | |
| Demographic characteristics in 2017 | | | | | | | | |
| Age (mean, sd) | | | | | | | | |
| Gender (n, %) | | | | | | | | |
| Insurance payment (n, %) | | | | | | | | |
| Demographic characteristics in 2019 | | | | | | | | |
| Age (mean, sd) | | | | | | | | |
| Gender (n, %) | | | | | | | | |
| Insurance payment (n, %) | | | | | | | | |

Note Group A Diabetes with cardiovascular disease, chronic kidney disease or at high cardiovascular risk; Group B Diabetes without cardiovascular disease, chronic kidney disease or at high cardiovascular risk; Group C Non-diabetes with cardiovascular disease, chronic kidney disease or at high cardiovascular risk; Group D Non-diabetes without cardiovascular disease, chronic kidney disease or at high cardiovascular risk;

2) The clinical characteristics of the studied population of the latest visit for all patients, as well as the trends for inpatients over time (2015, 2017, and 2019 respectively). Clinical characteristics of outpatients and hospitalized patients will be described respectively.

Table 3. The clinical characteristics of the latest visit

| Outpatients | | | | Inpatients | | | | Total patients |
|---|----------------|----------------|----------------|-------------------|----------------|----------------|----------------|-----------------------|
| Group A | Group B | Group C | Group D | Group A | Group B | Group C | Group D | |
| Clinical characteristics in 2015 | | | | | | | | |
| Department of discharge | | | | | | | | |
| Death | | | | | | | | |
| Clinical characteristics in 2017 | | | | | | | | |
| Department of discharge | | | | | | | | |
| Death | | | | | | | | |
| Clinical characteristics in 2019 | | | | | | | | |
| Department of discharge | | | | | | | | |
| Death | | | | | | | | |

Table 4. The laboratory measurement of the latest visit

| Outpatients | | | | Inpatients | | | | Total patients |
|--------------------|----------------|----------------|----------------|-------------------|----------------|----------------|----------------|-----------------------|
| Group A | Group B | Group C | Group D | Group A | Group B | Group C | Group D | |
| | | | | | | | | |
| | | | | | | | | |

Clinical characteristics in 2015

HbA1c
Random blood glucose
Serum creatinine

[figure not shown]
Clinical characteristics in 2017

[figure not shown]
HbA1c
Random blood glucose
Serum creatinine

Clinical characteristics in 2019

HbA1c
Random blood glucose
Serum creatinine

Note Group A Diabetes with cardiovascular disease, chronic kidney disease or at high cardiovascular risk; Group B Diabetes without cardiovascular disease, chronic kidney disease or at high cardiovascular risk; Group C Non-diabetes with cardiovascular disease, chronic kidney disease or at high cardiovascular risk; Group D Non-diabetes without cardiovascular disease, chronic kidney disease or at high cardiovascular risk;

7.3 Covariates

No applicable. This is a cross-sectional study aiming to describe the proportion, clinical characteristics and economic burden.

8. DATA SOURCES

Tianjin regional database covers individual-level health information from hundreds of public hospitals. There were 40 tertiary hospitals, 32 secondary hospitals and 276 community hospitals Tianjin. Through integrating EMR systems of hospitals by patient unique identify code, the database contains comprehensive information regarding clinical care, such as patients' basic information, medical advice, diagnosis, laboratory examination, medical records and medical costs. It could be a valuable big data resource for clinical studies. There were approximately 600,000 patients diagnosed with diabetes in 40 tertiary hospitals from 01/01/2015 to 31/12/2019. Of these, 10,000 patients were with comprehensive information through integrating EMR systems.

9. DATA MANAGEMENT AND SOFTWARE/TOOLS

9.1 Software/Tools

PL/SQL version 13.0.2.1898 for data extraction at first step;
R version 4.0.3 for further data cleaning, transformation and data analysis;
All operation will be carried out on the elastic-compute-services.

9.2 Handling of Missing Values

We will clean data using transparent and prespecified rules, including the development of variable dictionaries, standardization of medical texts, and approaches to inconsistent data and outliers. A multidisciplinary research team will be assembled for developing the rules, including epidemiologists, statisticians, and clinical experts.

9.3 Handling of Inconsistencies in Data and Outliers

We will clean data using transparent and prespecified rules, including the development of variable dictionaries, standardization of medical texts, and approaches to inconsistent data and outliers. A multidisciplinary research team will be assembled for developing the rules, including epidemiologists, statisticians, and clinical experts.

10. DATA ANALYSIS

10.1 Main analysis

The analyses will mainly describe the patient demographic characteristics, comorbidities, complications, treatment pattern and economic burden based on 40 hospitals EMRs of Tianjin regional database.

Characteristics presented as continuous data will be summarized through means, standard deviations, medians, minimum and maximum values; whereas, categorical data will be summarized as counts and proportions.

All tests of statistical significance among different subgroups (age, gender, department, underlying diseases, etc.) will be two-sided unless otherwise specified; any test resulting in $p < 0.05$ will be considered statistically significant. Student-t test, analysis of variance, chi-square test and other rank test will be mainly applied for this study.

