### **9.7.1 Main analysis**

Before analyses start, 200 randomly selected medical chart will be fully reviewed by well-trained experts to validate the accuracy and sensibility of code used to identify patients with cardiovascular disease or at high cardiovascular risk, chronic kidney disease and type 2 diabetes. This QC procedure for database study would be performed by [REDACTED].

The analyses will mainly describe the patient demographic characteristics, comorbidities, treatment pattern and economic burden based on 40 hospitals EMRs of Tianjin regional database. Descriptive data will be provided. The statistical methods and analyses will be described in detail in a Statistical and Epidemiological Analysis Plan (SEAP) prior to the commencement of any analyses.

Characteristics presented as continuous data will be summarized through means, standard deviations, medians, minimum and maximum values, whereas, categorical data will be summarized as counts and proportions.

All tests will be two-sided unless otherwise specified

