1.1 Does the protocol specify timelines for				
1.1.1 Start of data collection 				6
1.1.2 End of data collection 				6
1.1.3 Progress report(s)				6
1.1.4 Interim report(s)				6
1.1.5 Registration in the EU PAS Register®				6
1.1.6 Final report of study results.				6

Comments:

--

Section 2: Research question	Yes	No	N/A	Section Number
2.1 Does the formulation of the research question and objectives clearly explain:				7& 8& 9

 Date from which information on the first study is first recorded in the study dataset or, in the case of secondary use of data, the date from which data extraction starts.

 Date from which the analytical dataset is completely available.

Section 2: Research question	Yes	No	N/A	Section Number
2.1.1 Why the study is conducted? (e.g. to address an important public health concern, a risk identified in the risk management plan, an emerging safety issue)				7
2.1.2 The objective(s) of the study?				8
2.1.3 The target population? (i.e. population or subgroup to whom the study results are intended to be generalised)				9.2.2
2.1.4 Which hypothesis(-es) is (are) to be tested?				
2.1.5 If applicable, that there is no a priori hypothesis?				

Comments:

Section 3: Study design	Yes	No	N/A	Section Number

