6. RESEARCH METHODS

6.1 STUDY DESIGN

This study is an observational, cross-sectional study based on a routinely collected database. We constructed four groups for comparison: the group A and group B included all diabetic patients with/without established CV disease, CKD, or at high CV risk, respectively. The group C included all non-diabetic patients with established cardiovascular disease, chronic kidney disease, or at high cardiovascular risk. The group D will be constructed to match group A, non-diabetic patients will be included without established cardiovascular disease, chronic kidney disease, and not at high cardiovascular risk. For group D, we will randomly sample study populations to acquire a 1:1 sample of non-diabetic patients without disease by matching on age and gender with group A.

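### SAP 10.1 calls any p < 0.05 significant across an open-ended set of subgroup tests, in a study planned as descriptive and with no exploratory label in the visible text

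*SAP*

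**What the plan says.** SAP 10.1 plans summary statistics and then adds significance testing: "All tests of statistical significance among different subgroups (age, gender, department, underlying diseases, etc.) will be two-sided unless otherwise specified". It continues that "any test resulting in $p < 0.05$ will be considered statistically significant", and on methods that "Student-t test, analysis of variance, chi-square test and other rank test will be mainly applied for this study". The factor list is open, and no test is assigned to a variable or a contrast. SAP 6.1 says "We constructed four groups for comparison" but names no comparison between them.

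The protocol reads differently. Section 9.7.1 says "Descriptive data will be provided" and adds only that tests are two-sided; the 0.05 rule appears in the SAP alone. In the protocol's Annex 2 checklist, the item "2.1.4 Which hypothesis(-es) is (are) to be tested" is ticked N/A, measures of association (3.4) are N/A, and stratified analyses (10.4) are ticked No. SAP 7.3 also gives the aim as description.

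Both documents rank outcomes as primary, secondary and further, but neither connects that ranking to the tests.

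**The concern.** The SAP attaches a decision rule to comparisons for which the protocol states no hypothesis. As written, every subgroup difference that crosses 0.05 earns the same label, whether it is one of four comparisons or one of several dozen. The 5% applies to each test separately; it is not the error rate of any table or set of results that the study will present.

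Because the factor list is open and no contrast is named, the differences that receive the label can also be chosen after the data are seen. Protocol section 12 plans a journal paper and a congress presentation, so the label would reach readers who cannot tell how many tests lay behind it.

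The data set is also large. At this size the 0.05 threshold separates important from unimportant differences poorly, even when every difference is real.

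**Working it through.** The plan has no power, sample-size or family-wise figure to reproduce. Its only stated number is the two-sided 0.05 per test in SAP 10.1. The rest is illustration.

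**Inputs from the documents**
- Subgroup factors: 4 named (age, gender, department, underlying diseases), plus the open etc. (SAP 10.1).
- Variables in SAP Tables 2 to 4: 8 (age, gender, insurance; discharge department, death; HbA1c, random glucose, serum creatinine).
- Years: 3, from "as well as the trends for inpatients over time (2015, 2017, and 2019 respectively" (SAP 7.2.2).
- Settings: 2, from "Clinical characteristics of outpatients and hospitalized patients will be described respectively" (SAP 7.2.2).
- Patients with comprehensive data: 100,000 in protocol 9.4 and 10,000 in SAP 8. Both figures count patients with diabetes.

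**Assumptions, because the documents are silent**
- The number of tests. I use 4 (one outcome across the four named factors) and 8 × 3 × 2 = 48 (one four-group test per variable, year and setting).
- The correlation between test statistics: 0 to 0.8, equal for all pairs.
- The share of true nulls: all of them at first, then fewer.

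**Chance of at least one false positive, all m nulls true**

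For independent tests it is 1 − 0.95^m. With m = 4: 1 − 0.95^4 = 0.185. With m = 48: 1 − 0.95^48 = 0.915.

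For common correlation ρ, condition on a shared standard normal factor u. Each test fails to reject with probability Φ((1.96 − √ρ·u)/√(1−ρ)) − Φ((−1.96 − √ρ·u)/√(1−ρ)). Raise this to the power m, average over u and subtract from 1.

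| Tests | ρ = 0 | ρ = 0.5 | ρ = 0.8 | Expected false positives (0.05 × m) |
|---|---|---|---|---|
| 4 | 0.185 | 0.156 | 0.114 | 0.2 |
| 48 | 0.915 | 0.613 | 0.295 | 2.4 |

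Discharge department and death may not apply to outpatients. That removes 2 × 3 = 6 tests and leaves 42, with 1 − 0.95^42 = 0.884 if independent.

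**When only some nulls are true (48 independent tests)**
- 25% true, 12 tests: 1 − 0.95^12 = 0.460.
- 10% true, about 5 tests: 1 − 0.95^5 = 0.226.

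**Smallest observed difference that the rule calls significant**

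Take two equal subgroups of n = N/2 (an assumed split, with N set to each document's patient count). The difference in proportions near 50% is 1.96 × √(0.5/n). The difference in means, in standard deviations, is 1.96 × √(2/n).
- N = 10,000, n = 5,000: 1.96 × √(0.5/5,000) = 0.0196, or 2.0 percentage points; 0.039 SD.
- N = 100,000, n = 50,000: 1.96 × √(0.5/50,000) = 0.0062, or 0.6 percentage points; 0.012 SD.

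**The case against.** Much can be said for the plan. The test counts are inferred: SAP 10.1 does not say that every year-by-setting cell is tested, and the shells of Tables 1 to 4 have no p-value column. The all-null case is implausible, because groups A to D are defined by diabetes, cardiovascular disease, kidney disease, hypertension and hyperlipidaemia. HbA1c, glucose and creatinine follow those definitions closely, and the protocol's own background expects diabetic patients to carry more risk. The primary outcomes are proportions to be described, with no null value. The outcomes are ranked, so some ordering exists. Finally, SAP numbering passes from 10.1 to 10.3, and the protocol's from 9.7.1 to 9.7.3, so a section in each is not visible.

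All of this stands as a limit on the size of the point. A reader might infer that false significant findings are nearly certain to be reported. The documents do not support that, since they give neither the number of tests nor the share of true nulls. With independent tests the chance passes 0.95 only at 59 or more true nulls. At correlation 0.5 it reaches 0.95 only if the 48 four-group tests are each split into 6 pairs (288 tests), which no passage plans. A reader might also infer that the protocol declares there is no hypothesis. It only states none: checklist item 2.1.5, on having no a priori hypothesis, is itself ticked N/A.

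The objection does not remove the rule. SAP 10.1 says that tests will be applied, leaves their range open and gives any p < 0.05 the same status.

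**Conclusion.** The point holds in a limited form. SAP 10.1 applies an unadjusted 0.05 rule to an open set of subgroup tests. Nothing visible links them to the outcome ranking, controls their number or marks them exploratory, and this sits badly with a descriptive study and with the checklist answers in 2.1.4, 3.4 and 10.4. The absence is asserted for the visible text only.

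The family-wise figures are upper bounds for the assumed test counts and correlations, because many of the nulls are expected to be false. At this sample size, the firmer consequence may be that small but real differences are called significant. The primary proportions are unaffected. What changes is the status that the report may claim for group and subgroup differences. It is a change to consider, justified mainly by its low cost.

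**What to change.** In SAP 10.1, delete the sentence part that makes every p < 0.05 statistically significant and put in its place:

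> The study is descriptive and tests no confirmatory hypothesis. All between-group and subgroup comparisons are exploratory. Differences are reported with 95% confidence intervals. Any p-values are nominal and unadjusted, are shown with the number of tests performed, and are not described as statistically significant.

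Replace the trailing etc. with a closed list of subgroups, and reconcile that list with checklist item 10.4.

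I would not add a designated main contrast. The protocol plans none, and a non-diabetic denominator built from group C plus group D would be distorted, because D is a 1:1 sample matched to group A. Nor would I require a multiplicity adjustment: it is a debatable trade-off in a descriptive study, and it addresses the number of tests, not the triviality of a difference.

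The cost is SAP wording plus interval estimates in the output; no new data are needed. The downside is that subgroup differences with nominal p < 0.05 can no longer be called significant.

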6.3 STUDY POPULATION

Diabetic/non-diabetic patients with/without established cardiovascular disease, chronic kidney disease, or at high cardiovascular risk.

Inclusion Criteria:

- 1) Patients in the Tianjin regional database from 01/01/2015 to 31/12/2019.
- 2) Group A: patients with diagnosis of diabetes, and with diagnosis of cardiovascular disease, heart failure, chronic kidney disease or at high cardiovascular risk;
- 3) Group B: patients with diagnosis of diabetes, but not with diagnosis of cardiovascular disease, heart failure, chronic kidney disease or at high cardiovascular risk;
- 4) Group C: patients with diagnosis of cardiovascular disease, heart failure, chronic kidney disease or at high cardiovascular risk, but not with diagnosis of diabetes;
- 5) Group D: patients without diagnosis of cardiovascular disease, heart failure, chronic kidney disease or at high cardiovascular risk, and without diagnosis of diabetes. We will randomly select a group of non-diabetic patients without any of the above diseases by matching on age and gender.

Definition of diabetes, cardiovascular disease, chronic kidney disease and high cardiovascular risk

- Diabetes: patients with at least 1 discharged diagnosis or 2 outpatient diagnosis of diabetes (ICD-10 E10-E14)
- Cardiovascular disease: patients with at least 1 discharged diagnosis or 2 outpatient diagnosis of ischemic heart diseases (ICD-10 I20~I25); or patients with at least 1 discharged diagnosis or 2 outpatient diagnosis of cerebrovascular diseases (ICD-10 I60~I69); or patients with at least 1 discharged diagnosis or 2 outpatient diagnosis of ischemic peripheral artery disease (ICD-10 E10.501, E11.603, E14.501, E14.606, E14.503, I73.9, I99.03, I99.04);
- Heart failure: patients with at least 1 discharged diagnosis or 2 outpatient diagnosis of heart failure (ICD-10 I50);
- Chronic kidney disease: inpatients with at least once 1 discharged diagnosis CKD (ICD-10 N18), or inpatients with the last estimated glomerular filtration rate (eGFR, calculated by CKD-EPI equation) <60 mL/min/1.73 m² or prescription of dialysis, but not with the diagnosis of acute kidney injury (ICD-10 N17); or outpatients with at least 2 diagnosis of CKD or with two consecutive eGFR (calculated by CKD-EPI equation) <60 mL/min/1.73 m² by 90 days or more.

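### SAP 10.1 names pooled-variance tests for laboratory values whose spreads and group sizes are likely to differ, so p values can be too small or too large at any sample size

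*SAP*

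**What the plan says.** SAP 10.1 applies tests to "All tests of statistical significance among different subgroups (age, gender, department, underlying diseases, etc".) and lists the methods: "Student-t test, analysis of variance, chi-square test and other rank test will be mainly applied for this study". Tests "will be two-sided unless otherwise specified", and "any test resulting in $p < 0.05$ will be considered statistically significant". Neither the SAP nor Protocol 9.7.1 mentions an unequal-variance version, a variance check, or a rule for choosing a rank test over a t test.

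SAP 6.1 sets up the groups: "We constructed four groups for comparison: the group A and group B included all diabetic patients", with and without the listed conditions. Group C is all non-diabetic patients with those conditions. Only Group D has a size rule: the plan will "acquire a 1:1 sample of non-diabetic patients without disease by matching on age and gender with group A".

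SAP 6.3 defines the groups by diagnosis, and CKD also by eGFR below 60 or dialysis. For example, "Group B: patients with diagnosis of diabetes, but not with diagnosis of cardiovascular disease, heart failure, chronic kidney disease or at high cardiovascular risk". The laboratory outcomes in SAP Table 4 are HbA1c, random blood glucose and serum creatinine, shown separately for outpatients and inpatients and for 2015, 2017 and 2019.

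**The concern.** Student's t test and ordinary ANOVA assume the same variance in every group. Here the groups are sorted on characteristics closely tied to the values then compared. A and B have diagnosed diabetes and C and D do not, which bears on HbA1c and glucose. A and C can contain CKD and dialysis patients, whom B and D exclude, which bears on creatinine through eGFR. Equal spreads would be a surprising assumption for these three outcomes.

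Unequal spread does most harm when group sizes also differ. Five of the six pairs among A to D have no size control, nor do departments or age bands. The 1:1 ratio of A to D is also not guaranteed within the setting and year cells of Table 4.

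What is at stake is the meaning of the 0.05 threshold for differences that are null or small. Some would be declared significant too often and others too rarely. This is separate from matching, clustering and multiplicity, and would remain with independent patients and a single test.

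**Working it through.** **Inputs.** From the documents: two-sided 0.05 (SAP 10.1); A:D of 1:1, the only size ratio given (SAP 6.1); about 600,000 patients with diabetes (SAP 8), used only as the largest N simulated. Assumed, because the documents give neither: SD ratios of 1.2 to 2 and size ratios of 1:3 to 1:10. The plan has no figure of its own to reproduce on this point.

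**Formula.** For two groups with sizes n1, n2 and SDs s1, s2:

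- True variance of the difference: V_true = s1²/n1 + s2²/n2.
- Pooled variance of the difference: V_pooled = [(n1·s1² + n2·s2²)/(n1 + n2)]·(1/n1 + 1/n2), which simplifies to s1²/n2 + s2²/n1. Pooling in effect divides each variance by the other group's size.
- Large-sample false-positive rate = 2·[1 − Φ(1.96·√(V_pooled/V_true))].

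If n1 = n2 or s1 = s2, the two variances agree and the rate is 5.0%. If both sizes are multiplied by the same number, the ratio does not change, so a larger N does not help.

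**Worked cases.**

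- Sizes 1:3, smaller group with 1.2 times the SD: V_pooled = 1.44/3 + 1 = 1.48; V_true = 1.44 + 1/3 = 1.773; √(1.48/1.773) = 0.914; 1.96 × 0.914 = 1.79; rate 7.3%.
- Sizes 1:10, smaller group with twice the SD: V_pooled = 4/10 + 1 = 1.4; V_true = 4 + 1/10 = 4.1; √(1.4/4.1) = 0.584; 1.96 × 0.584 = 1.145; rate 25.2%.
- Sizes 1:10, larger group with twice the SD: the two variances swap; √(4.1/1.4) = 1.711; 1.96 × 1.711 = 3.354; rate 0.08%.

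| Size ratio | SD ratio | Smaller group more variable | Larger group more variable |
|---|---|---|---|
| 1:1 | any | 5.0% | 5.0% |
| 1:3 | 1.2 | 7.3% | 3.2% |
| 1:3 | 1.5 | 10.7% | 1.7% |
| 1:3 | 2 | 15.0% | 0.8% |
| 1:10 | 1.2 | 9.1% | 2.3% |
| 1:10 | 1.5 | 15.7% | 0.7% |
| 1:10 | 2 | 25.2% | 0.1% |

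**Simulation** (normal data, 200,000 replicates, SD ratio 2, sizes 1:3). For total N from 60 to 600,000, Student's t test gave 14.9% to 15.2% when the smaller group was more variable and 0.7% to 0.9% when the larger was. Welch's t test gave 4.9% to 5.0% throughout.

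**Four-group ANOVA** (100,000 replicates, assumed sizes A 70,000, B 30,000, C 200,000, D 70,000). With twice the SD in A and B, as might hold for HbA1c, ordinary ANOVA gave 16.3%. With twice the SD in A and C, as might hold for creatinine, it gave 2.2%. Welch's ANOVA gave 5.0% and 5.1%. With four equal groups ordinary ANOVA gave 6.0% to 6.2%, so most of the error comes from the unequal sizes.

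**The case against.** The strongest reply is that nothing important rests on these p values. SAP 7.3 describes the aim as descriptive, the primary outcomes are proportions, the ENCePP checklist marks hypotheses and measures of association as not applicable, and the shell of SAP Table 4 has no p-value column. SAP 10.1 attaches its tests to subgroups and does not name A to D. All of this stands as a limit on importance. It does not remove the point: SAP 10.1 still sets a significance threshold, its subgroups include underlying diseases, and SAP 6.1 says the four groups are for comparison.

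A second reply is that the list of tests is not exclusive, that it includes rank tests, and that in R 4.0.3 (SAP 9.1) the default t.test and oneway.test are the unequal-variance versions. But the SAP names Student's test explicitly and gives no selection rule. Rank tests are themselves sensitive to unequal spread.

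Third, where spreads most clearly differ, such as HbA1c in diabetic against non-diabetic patients, the means are probably so far apart that either test gives p<0.05. That also stands.

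A reader might go further and infer that A against B on HbA1c, or B against D on creatinine, is already distorted. The documents do not support this. If A and B share one SD, a two-sample Student's t test between them holds 5%, and the same applies to B and D on creatinine. Distortion appears only if a pairwise contrast borrows the four-group ANOVA mean square, and the SAP specifies no pairwise procedure. In that case, take A, B, C, D shares of (25, 5, 45, 25), (40, 10, 10, 40) and (15, 3, 67, 15)%. With HbA1c SDs of 1.5–2.0 in diabetic and 0.4–0.5 in non-diabetic patients, the A–B false-positive rate would be 14% to 37%. With creatinine SDs of 60–100 against 15 µmol/L, the B–D standard error would be 2.9 to 6.1 times too wide. All these SDs and shares are assumptions.

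**Conclusion.** The point holds in conditional form. SAP 10.1 names pooled-variance tests for outcomes where unequal spread is likely and most group sizes are uncontrolled. Where both conditions occur, the real false-positive rate can lie well above or well below 5%, with the range shown in the table, whatever the sample size.

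Unequal spread is an inference from the definitions, and it concerns the three laboratory outcomes rather than every continuous variable. The size and direction of the error depend on SD and size ratios that the documents do not give. At the mild end (SD ratio 1.2, sizes 1:3) the departure is small.

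It would go too far to say that the p values are wrong as a matter of fact. A against D overall is equal in size and so is not affected by this fault. Nor are pairs of equal spread under a two-sample t test, the primary proportions, or the significance verdict where means are far apart. The point is worth acting on because the change is nearly free, not because it threatens the main results.

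**What to change.** In SAP 10.1, replace Student's t test and analysis of variance with Welch's t test and Welch's ANOVA. If pairwise contrasts are made, state that each standard error comes from the variances of the groups compared (for example Games-Howell) and not from a mean square shared across all four groups. Also state when a rank test will be used, and do not present it as the remedy for unequal spread.

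The cost is a sentence or two of SAP wording. No new data or software are needed: in R 4.0.3 the defaults of t.test and oneway.test already do this. If the variances are in fact equal, the loss of efficiency is negligible at these sample sizes.
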